Building on our promising feasibility data, the proposed K23 research study will examine the effects of ABM on cue-reactivity and cannabis outcomes in a four-session randomized, double-blind, sham-controlled pilot treatment trial. One-hundred and six (106) treatment-seeking adults with moderate to severe CUD will be randomized to receive either MET/CBT plus ABM or Motivational Enhancement Therapy/Cognitive Behavioral Therapy(MET/CBT) plus sham-ABM. An equal number of men and women will be recruited and randomization will be stratified by gender. ABM sessions will occur following each of the four weekly MET/CBT therapy sessions. Primary outcomes will include cannabis cue-reactivity and cannabis use.

Aim 1: Evaluate the efficacy of ABM combined with MET/CBT on reductions in cannabis cue-reactivity in adults with cannabis use disorder. Using a cue-reactivity paradigm, we will evaluate the efficacy of approach bias modification on physiological (i.e. skin conductance) and subjective (i.e. cannabis craving) cue-reactivity.

Hypothesis 1: Participants receiving ABM will demonstrate blunted cue-reactivity compared to control participants.

Aim 2: Evaluate the efficacy of ABM combined with MET/CBT on end of study cannabis use outcomes in adults with cannabis use disorder. Using self-report and urine toxicology we will evaluate the efficacy of ABM on cannabis use outcomes.

Hypothesis 2: Participants receiving ABM will demonstrate greater percent days abstinent and lower creatinine corrected cannabinoid levels compared to control participants.

Exploratory Aim 1: Explore gender as a potential moderator of ABM, cue-reactivity, and cannabis outcomes. Given existing evidence of gender differences in cannabis use, cannabis-related cognitive impairment, and

treatment outcomes, it is important to investigate the role of gender in interventions targeting cognitive processing, such as ABM. Pilot data suggests potential gender modification on cannabis outcomes in response to ABM.

B. BACKGROUND AND SIGNIFICANCE

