Experience with recruitment and retention of adults with CUD: [name] (primary mentor), has completed multiple NIH-funded studies involving individuals with CUD. Of immediate relevance to the proposed project, the candidate recently completed a 4-session human laboratory pilot study in non-treatment seeking adults with CUD. Over the course of approximately 8 months, a total of 61 patients were consented, of which, 49 were randomized, 39 (80%) completed all 4 study sessions, and 33 (67%) completed through follow-up. These studies demonstrate the ability to effectively recruit and retain individuals with CUD for brief interventions.

Experience with adjunctive treatments for psychosocial interventions: Developing adjunctive treatments for CUD has been a career research focus of primary mentor [name]. Most recently, she completed a pilot study on oxytocin-enhanced MET for cannabis dependence²⁶. Participants who received MET plus oxytocin demonstrated reductions in amount (grams) used daily ($p=0.012$) and number of cannabis sessions per day ($p=0.003$), while those who received MET plus placebo did not. In addition to [name] experience, off-site mentor [name] also has considerable expertise integrating psychosocial interventions with novel adjunctive treatment approaches (see *Biosketch*).

Experience with the ABM paradigm: The candidate recently completed a randomized sham-controlled pilot study investigating the effect of ABM in non-treatment seeking adults with CUD (N=33). Results showed a trend of blunted cannabis cue-induced craving at end of treatment among ABM participants compared to controls ($p=0.051$) (see Figure 1), and preliminary evidence of gender modification of cannabis outcomes; men receiving ABM reported fewer sessions per day at the end of treatment (EOT) compared to women ($p=0.022$), while there was no gender

difference in the sham-control group (Figure 2). These pilot findings suggest that ABM may be efficacious in reducing cue-reactivity and improving cannabis outcomes, and that gender may

Figure 1: Cannabis craving by group and visit adjusted for baseline.

[figure not shown]
[figure not shown]

Figure 2: Cannabis use by gender and condition at EOT.

moderate this effect. As proposed in this K23 application, further investigation into the feasibility and efficacy of ABM as a potential adjunct to psychosocial treatments is warranted.

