models will be used to estimate each parameter and variance estimate of ABM or sham-ABM on cue reactivity measured at EOT and FU visit. Model based means and associated standard errors will be used to assess treatment group differences at EOT and FU. These methods are particularly well suited in instances where missing data is present. Aim 2 is to evaluate the efficacy of ABM on the reduction of cannabis use characteristics between BL and EOT/FU, as well as the variance around each estimate. Cannabis use data will be collected using the TLFB (proportion of use days, abstinence) and creatinine-adjusted cannabinoid levels (CN-THCCOOH) and will be compared between treatment groups using GLM models with appropriate distributional assumptions. Study data will be modeled as time invariant summary measures of the use at the end of the 4-week study period. Secondarily, we will also assess the efficacy of ABM on abstinence at FU (four-week abstinence). Study abstinence will be determined using UDS results (≤ 50 ng/ml) in concert with daily self-reported use. Exploratory Aim 1 will investigate the influence of gender on the treatment outcome and parameter estimates. Model interaction terms between study treatment assignment and gender will be added to each model developed for study aims 1 and 2 and tested for evidence of effect modification. When gender modification is present, pairwise comparisons within and across groups will be examined to assess the direction and magnitude of the modification. Additional analysis will assess neuropsychological data between groups over time using GLM models with appropriate distributions. Relative improvements over time associated with ABM will be assessed using between group comparisons taken at EOT and FU visits while controlling for baseline response data. Continuous outcome data will be assessed using a Gaussian distribution and count data will be assessed using a Poisson distribution. Second, neuropsychological data will be incorporated in the primary outcome models using interactions with treatment assignment to assess possible moderating effects on reported cannabis craving and use. Lastly, when ABM shows a significant relationship with changes in cannabis craving and use, neuropsychological measures will be assessed for mediating effects on the significant outcomes using bootstrap methods⁴⁵. All analyses will be conducted using SAS v. 9.4.

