Statistical Power and Sample Size: The proposed study is largely focused on obtaining preliminary data to inform and power a larger randomized controlled trial to assess ABM for CUD. However, the proposed sample size will allow for adequate power to assess the primary study aims. Primary AIM 1: Evaluate the efficacy of ABM combined with MET/CBT on cue-reactivity in adults with CUD. In a previous pilot study, we found evidence of greater reductions in cue induced cannabis craving at the end of treatment in those receiving active ABM as compared to sham ABM (MCQ: 43.2 ± 1.0 vs. 39.5 ± 1.0 , $\Delta = 3.7 \pm 1.4$, $d = 0.58$). We assume that the effect will be similar in the proposed study; however, we will measure use during the final treatment visit as well as at the FU visit. Under a correlated measures model assumption with a conservative within subjects correlation of $\rho = 0.8$, a sample size of 84 participants would be necessary to detect the noted treatment effect size with 80% power and a type 1 error rate of 5%. To account for an expected attrition of 20% based on our pilot study we have inflated our sample size to **106 participants (n=53 in each treatment assignment)**. To achieve a randomized sample of 106 participants, we will need to enroll one hundred and thirty-six (136) participants. With a randomized sample of 106 participants, our 80% confidence interval around the sample estimated variance will be within 18% of the true population variance and the conservative upper estimate of the variance will be used to inform the power of the larger R01. Primary AIM 2: Evaluate the efficacy of ABM combined with MET/CBT on cannabis outcomes in adults with CUD. Cannabis use will be measured by a combination of self-reported use days and (CN-THCCOOH) levels measured following the 4th week of treatment. The sample size of 53 randomized participants (42 completers) in each treatment group necessary to provide adequate power in Aim 1 will provide 80% power with a type 1 error rate of 5% to detect a similar effect size to Aim 2 ($d = 0.58$) in EOT (CN-THCCOOH) levels between study groups under similar model assumptions. The sample size of 42 completers per group will provide 80% power with a type 1 error rate of 5% to detect an 18% decrease in the proportion of use days in the ABM (39%) as compared to Sham (57%). Thus, a **total randomized sample size of n=106** participants will provide adequate power to address the clinically meaningful study aims in a statistically efficient manner.

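### The direction and size of gender moderation are examined only if moderation is judged present; the threshold is unstated and no estimates are promised otherwise

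*Combined protocol and SAP*

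**What the plan says.** Section A labels the gender question exploratory: "Exploratory Aim 1: Explore gender as a potential moderator of ABM, cue-reactivity, and cannabis outcomes". The design gives it some weight: "An equal number of men and women will be recruited and randomization will be stratified by gender". Section E (Sample characteristics) ties the equal enrolment to the exploratory gender analyses.

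Section D5 (Study Aims) sets out two steps. The first is unconditional: "Model interaction terms between study treatment assignment and gender will be added to each model developed for study aims 1 and 2 and tested". The second is conditional: "When gender modification is present, pairwise comparisons within and across groups will be examined to assess the direction and magnitude of the modification".

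The plan does not say what significance level, or other criterion, makes modification present. It does not say that the interaction estimate, or the ABM-minus-sham difference in each gender, will be reported with an interval whatever the test shows. Section D5 (Statistical Power and Sample Size) gives no power for the interaction. That section also describes the study as largely a source of preliminary data for a larger randomised trial.

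**The concern.** A planning study serves its successor best with unselected estimates and honest intervals. Under the two-step rule, the effects in men and in women are looked at only after the interaction has cleared some bar. At this sample size an interaction must look very large to clear a conventional one. Estimates that pass will tend to overstate the true moderation. When the test fails, no gender-specific result is planned, although the trial recruits equal numbers of men and women for this purpose.

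The phrase about comparisons within and across groups is also loose. D5 uses groups for treatment arms, so comparisons within groups can naturally include men versus women inside one arm. Gender is not randomised, and such a contrast mixes any general gender difference with moderation. The quantity that measures moderation is ABM minus sham in men compared with ABM minus sham in women.

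**Working it through.** **Inputs.** From D5 (Statistical Power and Sample Size): effect size 0.58 SD; within-subject correlation 0.8; two post-baseline visits (end of treatment and follow-up); 84 completers, 42 per arm; 106 randomised, 53 per arm; 80% power; 5% type 1 error. From section A: equal numbers of men and women. Assumptions of this check: two-sided testing, a 5% threshold for the interaction, continuous outcomes, and the size of the true interaction, none of which the documents give for this analysis.

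**1. Reproduce the plan's figure.** The mean of two measures with correlation 0.8 has SD √((1 + 0.8)/2) = √0.9 = 0.949. Then n per arm = 2 × [0.949 × (1.960 + 0.842)/0.58]² = 42.0, so 84 in total. With 20% attrition, 42/0.8 = 52.5, rounded up to 53 per arm, or 106. Both figures match. A single measure would need 47 per arm two-sided or 37 one-sided, so the two-visit, two-sided form is the one that fits.

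**2. Standard error of the interaction.** There are 84/4 = 21 completers per gender-by-arm cell. The interaction is a difference of two differences, so four cell variances add:

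SE = 0.949 × √(4/21) = 0.414 SD.

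**3. Smallest observed interaction that passes.** 1.96 × 0.414 = 0.81 SD, which is 0.81/0.58 = 1.4 times the planned main effect.

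**4. Chance of passing, and average exaggeration when passed.** With t = true interaction/SE:

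- P(pass) = Φ(t − 1.96) + Φ(−t − 1.96)
- exaggeration = E(|estimate| given pass)/true value

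For 0.58 SD, t = 0.58/0.414 = 1.40, so P(pass) = Φ(−0.56) plus a negligible term, or 0.29. The truncated-normal mean gives an exaggeration of 1.85. A simulation agrees (0.287 and 1.84).

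| True interaction (84 completers, two visits, 5%) | P(pass) | Exaggeration |
|---|---|---|
| 0.29 SD | 11% | 3.5 |
| 0.58 SD | 29% | 1.85 |
| 0.87 SD | 56% | 1.34 |
| 1.16 SD | 80% | 1.12 |

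**5. Sensitivity at 0.58 SD.**

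| Variation | P(pass) | Exaggeration |
|---|---|---|
| All 106 analysed (26.5 per cell, SE 0.369) | 35% | 1.67 |
| One measure per subject, 84 completers (SE 0.436) | 26% | 1.93 |
| 10% threshold, 84 completers, two visits | about 40% | about 1.7 |

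The one-measure row is closer to Aim 2, where use is summarised once at the end of the four weeks.

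**6. Precision if always reported.** The 95% half-width is 1.96 × 0.414 = 0.81 SD for the interaction, and 1.96 × 0.949 × √(2/21) = 0.57 SD for ABM minus sham within one gender.

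**7. Men versus women inside one arm.** Suppose there is no interaction but a gender difference of 0.5 SD in both arms (illustrative). Each within-arm contrast has SE 0.949 × √(2/21) = 0.293 SD and is significant with probability 0.40. It is significant in exactly one arm with probability 2 × 0.401 × 0.599 = 0.48. This is before any interaction test is applied, so it shows only why the contrast cannot stand alone.

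**The case against.** The strongest reply is that the interaction term is fitted in every Aim 1 and Aim 2 model. For a continuous outcome, its coefficient is the difference in ABM effect between the genders. A reader might infer that the plan leaves moderation unestimated. The documents do not support that: only the follow-up comparisons are conditional. What is missing is a commitment to report the estimate and the gender-specific effects.

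Second, the plan states neither a 5% criterion nor an expected interaction of 0.58 SD, and it does not say that null results will be withheld. This stands. The percentages are conditional illustrations, and for a very large interaction the problem nearly vanishes. A looser threshold reduces the problem but, at 10%, does not remove it. Leaving the criterion unstated is itself a gap.

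Third, a reader might infer that the team will treat a one-arm gender contrast as proof of moderation, because section C reports from the pilot that "men receiving ABM reported fewer sessions per day at the end of treatment (EOT) compared to women". The inference goes too far. The pilot also reported no gender difference under sham, and it was a separate study. In this plan the evidence for moderation is the interaction test, and the wording on comparisons also admits ABM versus sham within each gender. The loose wording merits a clarification, no more.

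Fourth, a reader might extend the criticism to the mediation analysis, which runs only "when ABM shows a significant relationship with changes in cannabis craving and use". That is a separate methodological choice. At the planned effect of 0.58 SD the condition would be met about 80% of the time, and the documents contain nothing that contradicts it. It is not part of this point.

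**Conclusion.** The concern holds as a matter of estimation and reporting in an exploratory aim. Assessment of direction and size depends on an unstated criterion, and no estimates are promised when that criterion is not met. For an interaction as large as the planned main effect, the variations above give a chance of passing between 26% and 40% and an average exaggeration between about 1.7 and 1.9 times. On the plan's own two-visit basis with a 5% threshold the figures are 29% and 1.85. The chance of passing stays below one half for any true interaction under about 0.81 SD. These figures rest on a two-sided test, continuous outcomes, equal cells and an interaction size chosen for illustration. The primary comparisons, their error rate and the sample size are not affected.

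**What to change.** Replace the conditional sentence in D5 (Study Aims) with:

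> For every Aim 1 and Aim 2 outcome, the ABM-minus-sham difference in men, in women, and the difference between them (the interaction) will be reported with 95% CIs regardless of the interaction p-value, as exploratory; a men-versus-women contrast within a single arm will not by itself be taken as evidence of moderation.

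The cost is wording only, since the estimates come from interaction models that are already planned. No extra data or participants are needed. The downside is longer exploratory tables with wide intervals, about ±0.8 SD for the interaction, which is an accurate picture of what the trial can say about gender.

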B2. Cognitive mechanisms of addiction. Cognitive models of addiction identify two distinct yet interactive types of mental processes, implicit and explicit⁶⁻⁸. Implicit refers to automatic, reward-driven, contingency-based learning processes, while explicit refers to reflective, inhibitory, executive control-related processes^{7,9}. Chronic drug use results in neuroadaptations that strengthen the implicit reward-driven system and weaken the explicit control-related system, resulting in compulsive drug use despite negative consequences^{9,10}. Cannabis use is associated with explicit processing deficits including working memory, attention, and abstract reasoning¹², as well as maladaptive implicit processes, such as attentional bias¹³ and approach bias¹⁴. These implicit cognitive biases develop when drug-related stimuli acquire incentive-motivational properties following repeated exposure and sensitization of meso-corticolimbic reward pathways¹⁵. Cognitive biases are associated with heavier cannabis use, dependence severity, and more cannabis-related problems^{16,17}, and quantity of cannabis use has been associated with reward pathway hypersensitivity¹⁸. A review of twenty-four clinical fMRI studies found that attenuation of reward pathway sensitivity through cognitive interventions is a common factor associated with positive treatment outcomes across substances¹⁹, and therefore, is an important therapeutic target. Cognitive bias modification is a novel approach that targets reward pathway sensitivity using computerized tasks to reduce the incentive-salience of drug stimuli.

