D4.e. Cue Reactivity: Cue reactivity will consist of physiological (skin conductance) and subjective (self-reported craving) components and will be assessed at three time points: BL, EOT, and FU. Participants will be connected to a finger sensor and then exposed to a neutral cue set, followed by a cannabis cue set. Each cue set contains tactile, auditory, and olfactory cues. Cannabis craving will be assessed prior to neutral cues, after neutral cues, and after cannabis cues to account for any carryover effects³³. Skin conductance will be assessed continuously with time markers of cue onset/offset noted by study personnel to be used for subsequent analysis. Cue reactivity will be assessed following approach bias assessments.

D4.f. Additional instrumentation:

Descriptive assessment of cannabis use: Cannabis use in the 30 days prior to baseline will be assessed using urine drug screens and the Timeline Follow-Back (TLFB)³⁴. The TLFB is a calendar-based instrument used with specific probes to ascertain detailed information about amounts of substance use. Number of discrete cannabis using sessions per day and quantity (hits) used per day will be recorded.

If necessary to limit person-to-person exposure, certain items such as the HAM-A, HAM-D and questions about substance use may be completed remotely. Participants may also be sent survey links to complete questionnaires remotely throughout study participation.

Menstrual History Diary: Subjects will be asked to estimate the timing of their cycle for the 90-days prior to study entry and to track their cycle during study participation.

Substance-related instruments: **TLFB:** Described above. In addition to cannabis use, participants will be asked about daily alcohol use (standard drinks), as well as instances (yes/no) of other substance use. **Urine Drug Screening:** Drug screens will be performed using the One Step Multi-Drug Test Dip Card (Drugconfirm™), a lateral flow chromatographic immunoassay for the qualitative detection of drug or drug metabolite in the urine at the following cutoffs (ng/ml): cocaine (300), amphetamines (1000), methamphetamine (1000), THC (50), opiates (2000), and benzodiazepines (300). Samples will then be sent to MUSC laboratory for cannabinoid quantification

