Neuropsychological assessments: Cognitive functioning will be assessed at BL, EOT, and FU to examine whether cognitive functioning is improved following the intervention or whether changes in cognitive functioning mediate treatment effect. To obtain additional measures of implicit cognitive bias, a cannabis adaptation of the dot-probe task that has shown sensitivity across substances of abuse^{40,41} will be used to assess cannabis attentional bias and a cannabis adaptation of the Implicit Association Task¹⁴ will be used to assess cannabis memory bias. Multiple forms of executive function shown to be impacted by SUDs will be assessed and which include: inhibitory control (Go No-Go task⁴²), working memory – verbal (WAIS-IV Digit Span Subscale) and nonverbal (N-Back⁴³) tasks. The Symbol Digit Modalities Test (SDMT)⁵⁴ measures sustained attention, response speed, and visuomotor coordination. It involves filling in a blank space below a symbol with the appropriate symbol-paired number as quickly as possible for 90 seconds.

D4.g. Six-Month Follow-up: Participants will complete a six-month follow-up either in person or over the phone. They will complete a TLFB, CWS, HAM-A, HAM-D, and review DSM-5 CUD symptoms from the M.I.N.I. neuropsychiatric interview. Participants will also complete the MJPS, PSQI, SF36 self reports in the Survey Mode of Redcap. Participants who do not complete the visit in person will be given the option to complete the surveys though a RedCap Survey Link sent though MUSC email. Participants who complete the visit in person will provide a UDS.

D4.h. Participant compensation: Participants will be compensated for attendance using an escalating contingency management (CM) schedule, cash bonuses, and a chip pick to maximize retention. Participants will be paid \$40 for the screening visit (\$20 for the interview and \$20 for the questionnaires/UDS). Participants will receive a cash incentive starting at \$20 at week 1 and increasing by \$5 each week; any missed session will reset the cash incentive to \$20. Participants will receive cash bonuses for completing baseline/week 1 (\$25) and week 4 (\$50) Participants will be apid \$50 at the one-month follow-up visit , and \$20 at the 6-month follow-up visit if completed in person. Participants who come to their visit and produce a negative saliva drug screen will also draw from a bowl

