containing 250 chips that are assigned a certain value. Two-hundred thirty chips denote a small amount (\$1.00), 18 chips denote a moderate amount (\$10.00), one chip denotes a large amount (\$50.00), and one chip denotes a jumbo amount (\$100.00). Participants will be allowed three draws at the screening visit if they provide a UDS and five draws at subsequent visits if their saliva drug screens are negative. Participants will be paid with a Greenphire ClinCard.

Total possible reimbursement is \$295/participant plus the sum of what is gathered from the chip pick.

[figure not shown]
D4.i. Confidentiality: Confidentiality of all research data will be maintained by keeping all data in a locked file, limiting access to the computer database to only study personnel, and by using patient code numbers/initials as opposed to names on all paperwork. Any requests for the release of patient information will be referred to the candidate.

D4.i. Study Timeline

	Screen	BL/ Wk1	Wk 2	Wk 3	Wk 4	1 Month FU	6 Month FU
MINI	x						
DSM-5 CUD criteria		x			x	x	x
Urine pregnancy test	x	x			x		
Urine cannabinoid test, TLFB, CWS, PSQI, Menstrual History, HAM-A, HAM-D	x	x	x	x	x	x	x
MJ Summary Sheet, Self-reports	x	x			x	x	x
Neuropsych testing, Digit Span, SDMT		x			x	x	
Approach Bias assessment, Cue reactivity			x		x	x	
Integrated Treatment (MET/CBT + ABM)*		x	x	x	x		

*Participants will receive three sessions of MET/CBT over the four weeks.

D4.j. Study visit flow chart

D5. Statistical Considerations.

General Analysis: Baseline clinical and demographic characteristics will be collected and contrasts performed between treatment groups. Continuous and ordinal characteristics will be compared using a Wilcoxon Rank-Sum test while categorical characteristics will be compared using a Pearson Chi-Square test. In addition to baseline treatment group differences, preliminary analysis of baseline characteristics will examine significant correlates of outcomes. Characteristics found to be significantly associated with the primary outcome measures, will be included as covariates in the initial stages of adjusted model development. All analyses will be performed on the intent-to-treat sample consisting of all randomized subjects.

Study Aims: Aim 1 is to evaluate the efficacy of ABM in the reduction of cannabis cue reactivity outcomes between BL and EOT/FU, as well as the variance around each estimate. Generalized linear mixed (GLM) effects regression

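### Mediation of 4-week use and end-of-treatment craving would rest on mediators measured no earlier than the outcome: label those results as associations and add a time-ordered analysis using the one-month follow-up

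*Combined protocol and SAP*

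**What the plan says.** - **Purpose.** D4.f (Neuropsychological assessments): "Cognitive functioning will be assessed at BL, EOT, and FU to examine whether cognitive functioning is improved following the intervention", and also to learn "whether changes in cognitive functioning mediate treatment effect".
- **Mediator timing.** In the Study Timeline, the row "Neuropsych testing, Digit Span, SDMT" is marked at BL/Wk 1, Wk 4 and the 1-month FU, with nothing at Wk 2 or Wk 3.
- **Craving timing.** D4.e says that cue reactivity, including craving, "will be assessed at three time points: BL, EOT, and FU". In the timeline its later marks are also at Wk 4 and the 1-month FU.
- **Use outcome.** D5, Aim 2: "Study data will be modeled as time invariant summary measures of the use at the end of the 4-week study period". The power paragraph describes self-reported use days and CN-THCCOOH "levels measured following the 4th week of treatment".
- **Later outcomes.** D5 also compares cue reactivity at FU and, secondarily, four-week abstinence at FU.
- **Mediation.** D5 (Study Aims), only where ABM is significantly related to changes in craving and use: "neuropsychological measures will be assessed for mediating effects on the significant outcomes using bootstrap methods". No mediator visit, outcome visit, lag or adjustment for earlier outcome values is stated.

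**The concern.** A mediator has to change before the outcome it explains. For 4-week use and EOT craving, the schedule offers no post-baseline cognitive measure before EOT. A bootstrap interval deals with the sampling error of the indirect effect and says nothing about its direction.

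The protocol itself makes the reverse direction plausible. B2 states: "Cannabis use is associated with explicit processing deficits including working memory, attention, and abstract reasoning". The battery in D4.f covers working memory and sustained attention. If ABM lowers use and lower use improves those scores by EOT, the estimated indirect effect is non-zero although cognition mediated nothing. The analysis runs only when ABM has worked on the outcome, which is when such a reverse path would be active. At stake is a claim about how ABM works, in a trial meant to inform later studies of cognitive interventions (D7).

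**Working it through.** **1. Order of measurement, outcome by outcome, with the EOT mediator**

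| Outcome | Position relative to the EOT mediator |
|---|---|
| 4-week use summary | Window ends at about the time the mediator is taken |
| EOT CN-THCCOOH | Same time point (after week 4) |
| EOT craving | Same visit |
| FU craving or cue reactivity | About one month later |
| FU four-week abstinence | About one month later |

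The first three cannot be ordered. The last two can.

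**2. The plan's own figure**

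D5 gives no power or effect size for mediation. The Aim 1 sample size reproduces and supplies the inputs below. With d = 0.58, within-subject correlation 0.8, two post-baseline measures, two-sided 5% and 80% power:

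n per arm = 2 × ((1.960 + 0.842)/0.58)² × (1 + 0.8)/2 = 41.998, so 42 per arm and 84 in total. Then 84/0.80 = 105, made even at 106. This neither supports nor weakens the point, which is about order.

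**3. What a same-visit analysis returns when cognition is only a consequence**

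Assumed model, standardised:
- EOT outcome Y = −0.58·T + e
- EOT cognition M = −b·Y + √(1 − b²)·e′
- FU outcome = 0.8·Y + 0.6·e″

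There is no path from M to any outcome. The value of b is not in the documents, so 0.3, 0.5 and 0.7 are assumed.

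The effect of T on M is 0.58b. The coefficient of M in the regression of Y on T and M is −b, because the covariance given T is −b and the variance of M given T is b² + 1 − b² = 1. The apparent indirect effect is therefore −0.58b², a share b² of the total effect: 9%, 25% and 49%. The true share is zero.

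Simulation: 84 completers, 400 trials per value of b, percentile bootstrap with 300 resamples, analysed only when ABM was significant on the outcome concerned.

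| b | Same visit: trials analysed | Mediation declared | FU outcome adjusted for EOT outcome: trials analysed | Mediation declared |
|---|---|---|---|---|
| 0.3 | 299 | 9.7% | 233 | 0.4% |
| 0.5 | 309 | 31.1% | 211 | 0.0% |
| 0.7 | 285 | 58.2% | 202 | 0.5% |

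In this model the EOT outcome was adjusted for in both the mediator and the outcome regression. Repeat runs shifted the percentages by several points without changing the pattern. Moving to the FU outcome without adjusting for the EOT outcome did not help, because the FU value carries the EOT value forward.

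**4. What the time-ordered model loses**

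Now let cognition truly carry the whole effect during treatment (paths 0.83 × 0.7 = 0.58, or 1.16 × 0.5 = 0.58), with the same 0.8 path from EOT to FU. The adjusted FU model then declared mediation in only about 4–7% of trials, and the same-visit model in 97–100%. Where cognition was assumed to go on acting after EOT, the adjusted FU model detected it in 87–98%. That figure depends on the size assumed for the continuing effect.

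**5. Participants with FU data**

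In the pilot (section C), 39 of 49 (80%) completed all sessions and 33 of 49 (67%) completed through follow-up. Applied to 106: 106 × 0.80 = 85 and 106 × 0.67 = 71.

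**The case against.** The mediation sentence fixes no pairing of visits. A reader might infer that the mediation analysis as a whole cannot separate cause from consequence. The documents do not support that: the significant outcomes may include FU craving and FU abstinence, and for these an EOT mediator comes first. This is an under-specified sentence, and nothing in the visit schedule has to change.

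Two further readings go too far. One is that every use day precedes the cognitive testing: D5 does not define the TLFB window or its order relative to week 4 testing, and week 4 still contains a treatment session. The other is that mediator and craving are certainly measured on the same day: the text says only EOT, and the shared visit is read from the Wk 4 column.

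The support for a reverse path is also limited. B2 reports an association and does not say that cognition recovers within four weeks of reduced use. It also links cognitive biases to heavier use, which fits the planned direction equally well.

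The strongest objection is to the remedy. Adjusting for the EOT outcome removes any mediation already completed during treatment, so the FU model answers a narrower question than the one in D4.f. Step 4 confirms this. The objection stands as a reason to supplement the same-visit analysis and not replace it. It does not give the same-visit analysis a direction.

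Finally, this is an additional, conditional and unpowered analysis in a pilot trial. That limits the consequence but does not remove it.

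**Conclusion.** The point holds for treatment-period use, EOT CN-THCCOOH and EOT craving: a bootstrap indirect effect through EOT cognition shows an association and cannot establish direction. It does not hold for FU craving or FU abstinence.

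The size of any false mediation depends on a use-to-cognition effect that the documents do not give. Under assumed paths of 0.3 to 0.7 it was declared in roughly 10% to 58% of trials with a significant ABM effect. These figures are illustrative: they come from one simple model without baseline covariates. The visit-order argument rests on the schedule alone and does not need them.

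This is a minor point about mechanism claims. No primary efficacy test, secondary efficacy test or sample size is affected.

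**What to change.** Add to D5, using data already scheduled:

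1. Report any analysis of an EOT mediator with treatment-period use, EOT CN-THCCOOH or EOT craving as a same-time association, not as evidence of mediation.
2. Add a time-ordered mediation analysis. Mediator: change from BL to EOT in each neuropsychological measure. Outcomes: cue reactivity at FU, use days or abstinence from EOT to FU, and CN-THCCOOH at FU. Adjust for the baseline mediator, the baseline outcome and the EOT outcome, and state which regressions include the EOT outcome.
3. State the limits of item 2. It tests only effects of cognition that continue after EOT. It has little power for mediation completed during treatment. It loses participants without FU data (about 71 of 106 against about 85, if the pilot rates recur). It remains open to unmeasured mediator–outcome confounding.

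The cost is a few sentences and one extra set of models, with no new visits or measures. A time-ordered analysis of 4-week use itself would need a cognitive assessment during treatment, which is not scheduled, and this point does not call for one.
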